11	Refe	erences	33

List of abbreviations used

AE	Adverse Event
AUROC	Area Under the Receiver Operating Characteristics
AVPU	Alert, Verbal, Pain, Unresponsive
ВР	Blood Pressure
CI	Confidence Interval
CRN	Clinical Research Network
C-Statistic	Concordance statistic
CTRU	Clinical Trials Research Unit
CXR	Chest X-ray
DNR	Do Not Resuscitate
ECG	Electrocardiogram
GCS	Glasgow Coma Score
НРА	Health Protection Agency
НТА	Health Technology Assessment
ICNARC	Intensive Care National Audit & Research Centre
LASSO	Least Absolute Shrinkage and Selection Operator
MI	Multiple Imputation
NHS	National Health Service
NIHR	National Institute for Health Research
ONS	Office for National Statistics
PCA	Principle Components Analysis
PMG	Project Management Group
POPS	Paediatric Observation Priority Score
ROC	Receiver Operating Characteristic
SAP	Statistical Analysis Plan
SOP	Standard operating procedure
SSC	Study Steering Committee
STARD	Standards for Reporting Diagnostic Accuracy
TRIPOD	Transparent Reporting of a Multivariable Prediction Model for Individual Prognosis or Diagnosis
WCC	White Cell Count
WHO	World Health Organisation

Study title	The PRIEST study: Pandemic Respiratory Infection Emergency System Triage			
Study design	Observational cohort study			
Study participants	People attending hospital emergency department with suspected respiratory			
	infections during the COVID-19 pandemic			
Sample size	The sample size will ultimately depend upon the size and severity of the			
	pandemic, we anticipate collecting data from 20,000 cases to identify 200 with an			
	adverse outcome.			
Follow-up	Follow up will be collected at 30 days post initial attendance.			
Statistical analysis	• Assess the performance of existing triage tools (CURB-65, PMEWS, The Swine Flu			
	Hospital Pathway, NEWS2, WHO pneumonia hospitalisation algorithm) for			
	predicting adverse outcome (death or needing respiratory, cardiovascular or			
	renal support) in patients with suspected pandemic respiratory infection			
	Investigate the predictive value of clinical characteristics and routine tests for			
	adverse outcome			
	Develop and internally validate new triage methods based on			
	 Presenting clinical characteristics 			
	 Presenting clinical characteristics, electrocardiogram, chest X-ray and 			
	routine blood test results			
	by developing a multivariable prediction model for adverse outcome			
	• Dependent on the number of cases and events, to externally validate the new			
	triage methods			

Figure 1: Study flow diagram

1 Introduction, study design and key study objectives

This statistical analysis plan (SAP) outlines the analysis to be performed for the hospital emergency department part of The PRIEST study. Planned analyses for the prehospital services (NHS 111 and 999) will be detailed in a separate SAP. This SAP will guide the Trial Statistician during the statistical analysis of all quantitative outcomes in order to answer the objectives of the study.

This SAP is written in conjunction with applicable statistical standard operating procedures from the University of Sheffield Clinical Trials Research Unit (CTRU) and study documents (Protocol and Data Validation Specification). It will adhere to the Transparent Reporting of a Multivariable Prediction Model for Individual Prognosis or Diagnosis (TRIPOD) statement [1] and the Standards for Reporting Diagnostic Accuracy (STARD) 2015 guidelines [2].

All analyses will be performed in a statistical software package such as STATA version 16 [3].

1.1 Study objectives

The specific objectives outlined in the protocol after each wave of the pandemic, for the hospital (emergency department) are:

- 1. To determine the discriminant value of emergency department triage methods for predicting severe illness in patients presenting with suspected pandemic respiratory infection
- 2. To determine the discriminant value of presenting clinical characteristics and routine tests for identifying severe illness
- 3. To determine the independent predictive value of presenting clinical characteristics and routine tests for severe illness
- 4. To develop new triage methods based upon presenting clinical characteristics alone or presenting clinical characteristics, electrocardiogram (ECG), chest X-ray and routine blood test results, depending upon the data available and the predictive value of variables evaluated in objective 3

2 Sample Size

The sample size will ultimately depend upon the size and severity of the pandemic. Our pragmatic data collection methods will ensure that we maximise any opportunity to evaluate emergency department triage methods in a pandemic.

Our experience in the 2009 pandemic has shown us that pre-pandemic estimates of case hospitalisation and case fatality rates can be very misleading and that sample size estimates must take into account considerable uncertainty in these estimates. Nevertheless, we have also shown that informative findings can be generated even in a pandemic with a very low rate of adverse outcome.

Given that most cases of suspected pandemic respiratory infection (even in a severe pandemic) do not result in an adverse outcome, the key variable in determining study power is the number of cases with an adverse outcome. A single cohort including at least 150 cases with adverse outcome would allow us to estimate the c-statistic of a triage method, clinical variable or test with a standard error of 0.03 (assuming the true c-statistic was 0.8). The table below shows the standard error resulting from samples with smaller numbers of adverse outcomes.

N with adverse outcome	Standard error (assuming c-statistic was 0.8)
150	0.033
125	0.036
100	0.040
75	0.046
50	0.056

A sample with N=150 adverse outcome would estimate the sensitivity of a dichotomised rule, variable or test with a standard error as outlined in the table below, depending on the sensitivity at the threshold used. Estimates of specificity would obviously be very precise given the anticipated low prevalence of adverse outcome.

Sensitivity	Lower limit of 95% Cl
1.00	0.98
0.95	0.90
0.90	0.84
0.85	0.78
0.80	0.73

The same cohort could be used to identify independent predictors of outcome and develop new triage methods (objectives 3 and 4). The number of variables that could be tested as independent predictors of outcome in a multivariable model and for inclusion in a triage method would depend upon the sample size. Based on the rule of thumb of needing at least 10 events for each independent regression variable in a

logistic regression, a cohort with 150 cases with adverse outcome would allow us to test up to 15 parameters [4].

These estimates assume that each triage method and predictor variable will be used and tested on the whole cohort. However, we plan to explore whether different patients require different triage methods, particularly whether a different triage method is required for children and adults. Data from the 2009 H1N1 pandemic suggest that around a quarter to a third of adverse outcomes may occur in children [5] [6]. To increase the probability that we will have at least 50 cases with adverse outcome among children we will aim to recruit a total of 200 cases with adverse outcome rather than 150.

If we assume that the prevalence of adverse outcome is the same as our 2009 cohort (1%) then we would need to collect data from 20,000 cases to identify 200 with an adverse outcome. We have therefore used this estimate in planning, although it is likely to be an overestimate of the total numbers required given the mild nature of the 2009 pandemic. A more severe pandemic would allow more precise estimates to be made with no additional costs or would allow us to reduce the total number of cases required to identify 200 with an adverse outcome.

If we are able to develop a new triage method that appears to have superior discriminant value to existing methods then we would want to validate this method in a new cohort. A sample including 421 cases with adverse outcome would provide 80% power to compare an area under the ROC curve of 0.85 versus 0.90 at 5% significance, assuming a correlation of 0.6 between scores. We have not included validation of a new triage method in our objectives because this would require (a) successful development of a new method and (b) a much larger sample size, with associated costs and assumptions about pandemic severity. However, if the pandemic is severe (i.e. the prevalence of adverse outcome exceeds 3%, so the number with adverse outcome exceeds 450) we will split the cohort into two equal cohorts to allow testing of existing rules and derivation of new rules on one half and validation of new rules, with comparison to existing rules, on the other.

We plan to collect data across 40 hospitals and have based our sample size calculation on the assumption of receiving 500 completed forms, including an average of 5 adverse outcomes, per hospital over the course of the pandemic.

3 Outcome measures

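### The planned standard errors for the c-statistic are binomial SEs of a proportion: an unlabelled worst-case bound, about 1.5 times the Hanley-McNeil value at the SAP's own prevalence

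*SAP*

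**What the plan says.** SAP section 2 (Sample Size) takes the number of adverse outcomes as the main driver of study power. It claims that no fewer than 150 events "would allow us to estimate the c-statistic of a triage method, clinical variable or test with a standard error of 0.03". The condition attached to this claim is a true value of 0.8. A table then gives the SE for 150 events and for four smaller numbers:

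| Events | SE in the SAP |
|---|---|
| 150 | 0.033 |
| 125 | 0.036 |
| 100 | 0.040 |
| 75 | 0.046 |
| 50 | 0.056 |

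No variance formula is named, no number of non-events is attached to the table, and nothing marks the figures as a bound. Later in the same section the SAP assumes a 1% prevalence of adverse outcome, on which basis "we would need to collect data from 20,000 cases to identify 200 with an adverse outcome". That is 99 non-events for each event.

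**The concern.** A c-statistic compares two samples, events and non-events, and its variance depends on both group sizes and on how the scores are distributed in each group. A table that depends only on the number of events and on A(1 − A) treats the c-statistic as if it were a proportion observed among the events.

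The c-statistic is the main measure for the existing triage tools (section 6.2), and this table is the first support offered for 150 events. A reader who uses it to judge what 50 or 100 events can show is given a confidence interval that is too wide. At 50 events, the 95% half-width is 1.96 × 0.056 = 0.110 from the SAP's figure and 1.96 × 0.0378 = 0.074 under Hanley-McNeil.

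**Working it through.** **Inputs, all from SAP section 2.** True c-statistic A = 0.8; events n1 = 150, 125, 100, 75, 50; prevalence 1%, so non-events n0 = 99 × n1.

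**Step 1: reproduce the SAP's figures.** Use the SE of a simple proportion, sqrt(A(1 − A)/n1) = sqrt(0.16/n1). For 150 events: sqrt(0.16/150) = 0.03266. The first four rows match the SAP to three decimals. The fifth is 0.05657, which rounds to 0.057, so the 0.056 in the table has been truncated. None of the AUC variance formulas tried gives this table.

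**Step 2: why this is a bound.** With many non-events, the c-statistic is close to the average, over events, of the share of non-events that each event outranks. Each share lies between 0 and 1 and the shares average 0.8, so their variance cannot exceed 0.8 × 0.2 = 0.16. It reaches 0.16 only if every event outranks either all of the non-events or none of them. A real score behaves better than that.

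**Step 3: Hanley-McNeil at 1% prevalence.**

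var = [A(1 − A) + (n1 − 1)(Q1 − A²) + (n0 − 1)(Q2 − A²)] / (n1 × n0), with Q1 = A/(2 − A) = 0.6667, Q2 = 2A²/(1 + A) = 0.7111 and A² = 0.64.

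For 150 events, n0 = 14,850:
- numerator = 0.16 + 149 × 0.02667 + 14,849 × 0.07111 = 0.16 + 3.97 + 1055.93 = 1060.06
- denominator = 150 × 14,850 = 2,227,500
- SE = sqrt(0.000476) = 0.0218

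| Events | SAP | sqrt(0.16/n1) | Hanley-McNeil, 1% | Binomial ÷ Hanley-McNeil |
|---|---|---|---|---|
| 150 | 0.033 | 0.0327 | 0.0218 | 1.50 |
| 125 | 0.036 | 0.0358 | 0.0239 | 1.50 |
| 100 | 0.040 | 0.0400 | 0.0267 | 1.50 |
| 75 | 0.046 | 0.0462 | 0.0309 | 1.50 |
| 50 | 0.056 | 0.0566 | 0.0378 | 1.50 |

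Under this method an SE of 0.033 is reached with about 66 events, and 0.03 with about 80.

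**Step 4: sensitivity to the assumptions, at 150 events.**
- Prevalence, with Hanley-McNeil: 0.0219 at 3%, 0.0222 at 10%, and 0.0256 even with one non-event per event. Holding the total at 20,000 gives 0.0218.
- Another approximation (Obuchowski), 1% prevalence: 0.0222.
- Score distribution, with normal scores in both groups and 1% prevalence: 0.0178 with equal SDs; 0.0219, 0.0244 and 0.0271 when the event SD is 1.5, 2 and 3 times the non-event SD.

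Against 0.0327, the binormal cases give ratios from 0.0327/0.0271 = 1.2 to 0.0327/0.0178 = 1.8. Prevalence matters little; the shape of the score distributions matters more.

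**Step 5: the neighbouring sensitivity table.** Exact (Clopper-Pearson) lower 95% limits at n = 150 are 0.976, 0.90, 0.84, 0.78 and 0.73 for sensitivities of 1.00, 0.95, 0.90, 0.85 and 0.80. They agree with the SAP's 0.98, 0.90, 0.84, 0.78 and 0.73. A binomial method is right there, because sensitivity is a proportion of the events.

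**The case against.** The best defence is that A(1 − A)/n1 is the largest variance possible whatever the score distribution, as long as events are the smaller group. A planner facing an unknown pandemic, with a list of tools, variables and tests of unknown distribution, might prefer a bound that needs no assumption on prevalence or score shape. This part stands: the figures are valid as a ceiling. It does not rescue the text, which gives the values as the SE that such samples would yield and never calls them conservative.

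A second objection is that 1.5 is a property of Hanley-McNeil and not a constant. This also stands. The SAP gives no score distribution, so the factor should be read with its range of roughly 1.2 to 1.8.

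A third is that no decision turns on the table. The 150-event figure is also supported by the sensitivity limits and by the allowance of 10 events per variable (15 parameters), and the target of 200 comes from wanting at least 50 events in children. This limits the consequence, but a stated precision figure should still be right.

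Several stronger readings are tempting and are not supported:
- **That all the planned precision figures are wrong.** The sensitivity limits are correct; only the c-statistic SEs are affected.
- **That text and table contradict each other at 150 events.** 0.03 is 0.033 rounded to two decimals.
- **That the error decides whether child, site or subgroup c-statistics are reported.** Sections 5.2, 6.4 and 6.7 speak only of sufficient or insufficient numbers, and no rule there uses these SEs. The models' c-statistics will carry 95% CIs (section 7.3.3), so the planning table does not affect their reported precision.

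**Conclusion.** The point holds for the c-statistic table and the 0.03 in the text. The figures are the binomial SE of a proportion, presented as the expected SE of an area under the ROC curve. At the SAP's 1% prevalence and a c-statistic of 0.8, Hanley-McNeil gives 0.022 instead of 0.033 at 150 events (95% half-width 0.043 instead of about 0.065) and 0.038 instead of 0.056 at 50 events. The match to the binomial formula is firm. The size of the overstatement is about 1.5 under Hanley-McNeil and about 1.2 to 1.8 for normal scores with an event SD of 1 to 3 times the non-event SD, which is an assumed range. The 50-event row is also off by 0.001 on the SAP's own formula.

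A reader might infer that the study is wrongly sized. The document does not support that: precision is understated, so the study is not too small on this account, and the event target has other grounds.

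**What to change.** In SAP section 2, replace the table and the 0.03 in the text with SEs from a named AUC variance method at the assumed prevalence. With Hanley-McNeil at 1%, the entries are 0.022, 0.024, 0.027, 0.031 and 0.038. State the c-statistic, the prevalence and the method beside the table, and note that the SE varies with the score distribution. If the present figures are kept alongside, label them as a distribution-free upper bound and correct the last row to 0.057. Leave the event target and the sensitivity table unchanged. The cost is one table and one sentence, with no effect on recruitment or analysis.

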6.5 External validation of prediction models and new triage tools

The population will be split into a development and validation cohort if at least 400 adverse outcomes are recorded (resulting in at least 200 events in each cohort). This will provide sufficient power for the triage tools to be validated [18]. We anticipate there will be insufficient events to split the child cohort and hence this population will not be split. The cohort will be split by date across certain sites. A table of characteristics for the development and validation cohort will be presented to show how the cohorts differ.

The final logistic regression models (both the initial assessment model and full model) will be externally validated by applying the predictive model and triage tools and assessing calibration, discrimination and net benefit in order to assess reproducibility. The validation cohort will also be used to compare the newly developed triage tools against the existing triage tool that performed the best in the development cohort (based on AUROC) by comparing AUROC for these tools.

In order to assess transportability of the new triage tools into different populations or settings, future cohorts must be used to examine heterogeneity in performance across different populations and settings.

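### The 421 events stated for 80% power in the new-versus-existing AUROC comparison do not match the cohort-split rule, whose two conflicting triggers can leave only 200 to 225 events for that comparison

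*SAP*

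**What the plan says.** Section 2 (Sample Size) gives the requirement: "A sample including 421 cases with adverse outcome would provide 80% power to compare an area under the ROC curve of 0.85 versus 0.90", with the remaining inputs "at 5% significance, assuming a correlation of 0.6 between scores". Sidedness, the ratio of non-events to events and the method are not stated.

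The same paragraph gives the split rule. If "the prevalence of adverse outcome exceeds 3%, so the number with adverse outcome exceeds 450) we will split the cohort into two equal cohorts", one half serves for testing existing rules and deriving new ones. The other serves for validating the new rules and comparing them with existing ones.

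Section 6.5 gives the rule again with another number: the population is split "if at least 400 adverse outcomes are recorded (resulting in at least 200 events in each cohort"). It calls this sufficient power for validating the tools, citing reference 18. It leaves the child cohort unsplit and plans, as a further use of the validation cohort, an AUROC comparison of the new tools with the best existing tool.

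The planning size in section 2 is "we would need to collect data from 20,000 cases to identify 200 with an adverse outcome", which agrees with 40 hospitals at 500 forms each. Section 2 also says that validation is not among the study objectives because of the sample size it would need.

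**The concern.** The 421 events are tied to a comparison that takes place in only one part of the split cohort. A trigger of 450 or 400 events in the whole cohort cannot put 421 events in that part. The two sections also disagree on when to split: with 400 to 450 events, section 6.5 splits and section 2 does not.

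The trigger decides whether the derivation data are halved, and the stated power will colour how the comparison is read. If 421 is right, a non-significant difference at the trigger would say little, yet could be taken to mean that the new tool has no advantage. If 421 is wrong, the SAP overstates what the comparison needs. In both cases the power figure in section 2 does not describe the planned analysis.

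**Working it through.** **Inputs.** From section 2: 421 events; 80% power; AUROC 0.85 and 0.90 (difference 0.05); 5% significance; correlation 0.6; trigger above 450; equal halves; 20,000 cases planned. From section 6.5: trigger of at least 400, so at least 200 per part. Assumptions: a two-sided test (the SAP does not say), and 0.6 taken as the correlation r between the two AUROC estimates.

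**1. Can 421 events be reproduced?** With variances V1 and V2 expressed per event,

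n = (1.960 + 0.842)² × (V1 + V2 − 2r√(V1·V2)) / 0.05², where (1.960 + 0.842)² = 7.849.

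- *A(1−A), the variance behind the SAP's own standard-error table.* √(0.8 × 0.2/150) = 0.033 and √(0.16/100) = 0.040, as in section 2. Here V1 = 0.1275 and V2 = 0.0900, so the variance of the difference is 0.2175 − 1.2 × 0.1071 = 0.0890 and n = 7.849 × 0.0890/0.0025 ≈ 279.
- *Hanley-McNeil* (Q1 = A/(2−A), Q2 = 2A²/(1+A)): 130 to 131 events at 1% to 3% prevalence (99 to 32 non-events per event), and 164 at 1:1.
- *Obuchowski binormal* (V = 0.0099·exp(−a²/2)·[(5a²+8) + (a²+8)/k], a = 1.414·Φ⁻¹(A), k non-events per event): at 3% prevalence V1 = 0.0644 and V2 = 0.0475, the variance of the difference is 0.0455 and n ≈ 143; at 1% n ≈ 141; at 1:1 n ≈ 214.

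Using the null variance in the significance term raises these to 143 (Hanley-McNeil) and 154 to 156 (Obuchowski) at 1% to 3% prevalence, and to 308 for A(1−A). None reaches 421.

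Near matches appear only if something is changed:

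- A(1−A) with r = 0.4 instead of 0.6 gives 414.
- The cruder A(1−A)(1/events + 1/non-events) with two non-events per event gives 419, but 282 to 288 at 1% to 3% prevalence.
- Obuchowski at 1:1 gives 2 × 213.5 = 427 if the figure is read as total patients, that is, about 214 events.

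**2. Events in the validation part.** 450/2 = 225; 400/2 = 200. If 421 stands, an equal split needs 2 × 421 = 842 events in total.

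**3. Power on the SAP's own anchor (421 events = 80%).** At a constant ratio of non-events to events the variance is proportional to 1/n, so

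Power(n) = Φ(2.8016 × √(n/421) − 1.960).

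| Events in validation part | Arises from | Two-sided | One-sided |
|---|---|---|---|
| 200 | trigger in 6.5 | 48.8% | 52.7% |
| 225 | trigger in section 2 | 53.5% | 56.9% |
| 300 | 3% of 20,000, halved | 65.7% | 67.5% |

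The one-sided column uses 1.645 + 0.842 and 1.645 in place of 2.8016 and 1.960.

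**4. Power at 200 and 225 events if 421 is set aside** (r = 0.6, two-sided): 66% and 71% with A(1−A); 77% and 82% with Obuchowski at 1:1; about 91% and 94% with Obuchowski at 3% prevalence.

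**5. The 3% condition.** 0.03 × 20,000 = 600. The 450 is 3% of 450/0.03 = 15,000, a cohort size given nowhere, or 450/20,000 = 2.25% of the planned one.

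**The case against.** The strongest reply is that the split rule may be adequate and only the 421 faulty. On most standard calculations 200 to 225 events give about 77% power or more. Read as a 1:1 total of patients, 421 would correspond to roughly 210 events, close to what the triggers deliver. This stands. A reader might infer that the split cannot deliver the comparison; the documents do not support that, because it presumes that 421 is a correct event count.

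Four further points limit the concern.

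- Both triggers are minima, so 200 to 225 is the floor and not the expected number.
- A reader might take the sufficiency statement in 6.5 to be contradicted by 421. That statement is about validating the tools and rests on reference 18, which is not at hand. The AUROC comparison is listed as an additional use, and 421 concerns that comparison alone.
- A reader might apply the 2009 child share of adverse outcomes (a quarter to a third, section 2) and conclude that adult halves would be far below 200. Section 6.5 can equally be read as requiring 200 adult events per part, and section 5.2 expects few child events. What stands is that the trigger does not say which events it counts.
- Section 2 allows fewer than 20,000 cases in a severe pandemic, so a 15,000 denominator is possible. It is nowhere stated.

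Validation is also outside the formal objectives. Both sections nevertheless commit to it once the trigger is met, so the rule and its power statement need to agree.

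**Conclusion.** The point holds as an internal mismatch. The stated requirement is 421 events, and the split rule leaves as few as 200 to 225 where the comparison is made. On the SAP's own figure that is about 49% to 54% power at the trigger, and about 66% if 600 events were reached. The two triggers contradict each other, and 450 is not 3% of the planned cohort. These last two statements need no power formula.

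Which number is at fault cannot be settled from the SAP. As an event count, 421 does not follow from the stated inputs at 1% to 3% prevalence; the methods tried give roughly 130 to 280 events (up to 308 with the null variance). The power figures of 49% to 66% therefore depend on accepting 421, on a two-sided test and on equal halves. The conclusion covers the new-versus-existing AUROC comparison only. It does not show that 200 events are too few for calibration, discrimination or net benefit.

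**What to change.** - Recompute the 421 with a named method. State the sidedness, the expected ratio of non-events to events, what the 0.6 correlation refers to, and whether the result counts events or all patients.
- Put one identical trigger in sections 2 and 6.5. Count it in adult events, since children are not split, and express it as the number required in the validation part itself.
- State the power or precision that this number gives for the AUROC comparison, or delete the 80%/421 claim.
- Correct the 3%/450 pairing so that it agrees with the planned 20,000, or name the denominator intended.

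The total of 842 applies only if 421 is confirmed as an event count. It should not be adopted before the recalculation, because a trigger set too high could forfeit a useful validation.

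The cost is one recalculation and a few lines of SAP text. No extra patients are needed. The drawback is that the stated power for the comparison may become less favourable.

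### Sections 2 and 6.5 of the SAP set different triggers for splitting the cohort (more than 450 events, equated with above 3%, versus at least 400), and at the planned 20,000 cases 3% is 600 events

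*SAP*

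**What the plan says.** Section 2 (Sample Size) plans on a 1% prevalence of adverse outcome, so that "we would need to collect data from 20,000 cases to identify 200 with an adverse outcome". The same total follows from its site plan of 40 hospitals, on "the assumption of receiving 500 completed forms, including an average of 5 adverse outcomes, per hospital". It then adds a conditional validation step for a severe pandemic, defined as the case where "the prevalence of adverse outcome exceeds 3%, so the number with adverse outcome exceeds 450". In that event, "we will split the cohort into two equal cohorts", one for testing existing rules and deriving new ones, the other for validating them.

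Section 6.5 (External validation) restates the step with another threshold: "The population will be split into a development and validation cohort if at least 400 adverse outcomes are recorded", described as "resulting in at least 200 events in each cohort". It has no prevalence condition. It also says that the child cohort will not be split, because too few events are expected there.

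Both sections are current text. Neither refers to the other, and neither says which governs.

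**The concern.** Section 2 joins a prevalence and a count as though one followed from the other, but at the planned total they do not match. Section 6.5 then uses a third value. A statistician applying the SAP to a given event count could be told both to split and not to split.

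The trigger settles two things. One is whether there is a validation cohort at all, and with it the comparison of the new tools against the best existing tool. The other is whether the adult models are developed on all adult events or on roughly half of them. A rule with that much effect should give one answer for any count. As written, someone would have to choose between the thresholds once the count is known, since section 4 has the proportion with an adverse outcome reported weekly to the study team.

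The population counted is also unclear. Section 2 speaks of the cohort without restriction, while section 6.5 leaves children out of the split but does not leave them out of the 400.

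**Working it through.** **Inputs**
- Planning prevalence 1% and target of 200 events: section 2.
- 40 hospitals, 500 forms and 5 events per hospital: section 2.
- Split if prevalence is above 3%, equated with more than 450 events: section 2.
- Split if there are at least 400 events, giving at least 200 per cohort, with children not split: section 6.5.
- Share of adverse outcomes in children, a quarter to a third: section 2.

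**1. The planned total reproduces**
- 200 / 0.01 = 20,000 cases.
- 40 × 500 = 20,000 forms, and 40 × 5 = 200 events.

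**2. The 450 does not reproduce from 3%** (events = prevalence × cases)
- 0.03 × 20,000 = 600, not 450.
- 450 / 20,000 = 2.25%.
- 400 / 20,000 = 2.0%.
- Total at which 3% equals 450: 450 / 0.03 = 15,000, which the SAP does not give.
- Total at which 3% equals 400: 400 / 0.03 = 13,333, also not given.

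**3. What each rule says at 20,000 cases**

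| Events | Section 6.5 (at least 400) | Section 2 count (above 450) | Section 2 prevalence (above 3%) |
|---|---|---|---|
| below 400 | no split | no split | no split |
| 400 to 450 | split | no split | no split |
| 451 to 600 | split | split | no split |
| above 600 | split | split | split |

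The second row is a conflict between sections. The third is a conflict inside section 2's own sentence.

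Below 15,000 cases the two parts of section 2 fall the other way. At 10,000 cases, for example, 3% is 0.03 × 10,000 = 300 events, so the prevalence condition can be met while the count is not.

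**4. Population counted**

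Suppose the 400 in section 6.5 means events at all ages.
- Child share one quarter: 400 × 0.75 = 300 adult events, or 150 per half.
- Child share one third: 400 × 2/3 = 267 adult events, or 133 per half.

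Neither gives the 200 per cohort that section 6.5 states. Reaching 400 adult events would need between 400 / 0.75 = 533 and 400 / (2/3) = 600 events at all ages. These figures assume that events divide evenly between the halves.

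**The case against.** Several points on the other side deserve weight.

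**The total is not fixed.** The SAP says that sample size will depend on the pandemic and that 20,000 is probably more than needed. 450 is exactly 3% of 15,000, so the author may have had a smaller total in mind. Also, in strict logic a prevalence above 3% of 20,000 does imply more than 450 events. This stands as far as it goes: a slip in multiplication is not proven. What is shown is that the denominator is missing and that the two conditions are not equivalent at the only total the SAP plans for.

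**The 450 may count adults only.** 600 × 0.75 = 450, and 600 × 2/3 = 400, so both thresholds could come from 3% of 20,000 with different child shares. The SAP does not say this, and if it were so the two values would still need reconciling.

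**The event count is the natural governing condition.** Section 2 calls the number of adverse outcomes the key variable. That is a fair reading and it limits the conflict between sections to 400 to 450 events. A reader might infer that the sections contradict each other all the way from 400 to 600. The SAP does not support that: from 451 upward, section 2's count agrees with section 6.5, and only section 2's own prevalence condition dissents.

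**Early stopping.** A reader might also infer that a severe pandemic would end collection at 200 events and put the split out of reach, since section 2 says that such a pandemic "would allow us to reduce the total number of cases required to identify 200 with an adverse outcome". That is one of two options in the sentence. The other is to gain precision at no added cost, which means collecting on. It is a permission, not a stopping rule, so there is no contradiction with the split.

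**Timing.** Nothing suggests that the split would be decided after model results are seen. Section 2 places derivation within one half, so the split comes before modelling. Any event-count trigger is applied once the count is known; the problem is having more than one.

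**Conclusion.** The point holds in a limited form. The SAP gives two event counts and one prevalence for a single decision, and they do not agree. At 20,000 cases they correspond to 400 events (2.0%), more than 450 (2.25%) and more than 600 (3.0%). The sections give opposite answers for 400 to 450 events, and section 2 is at odds with itself for 451 to 600. The difference between 450 and 400 does not depend on the total. The 600, the percentages and the upper end of the second range assume 20,000 cases.

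The population is a further gap. If all ages are counted, the 200 events per cohort would not be met in adults, with about 133 to 150 expected on the SAP's own child share, which comes from the 2009 pandemic and may not apply here.

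This should be fixed but is not critical. Section 2 says that validation of a new method is not among the objectives, the split is conditional, and internal validation by cross-validation and bootstrapping (section 7.3.4) is planned whether or not it happens. An event count above 600 at 20,000 cases would satisfy every version of the trigger, though the SAP plans for 200.

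**What to change.** - State one trigger, as an event count, in identical words in sections 2 and 6.5.
- Delete the 3% condition from section 2. If it is kept, give the total it refers to and the matching count: 600 at 20,000 cases, or 450 at 15,000.
- Say that the count refers to adult events in the adult primary analysis set, since children are not split. If 200 events per half is the aim, that means at least 400 adult events, divided so that each half does reach 200.
- Record the choice before the split is made.

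The cost is a wording change to two sections of the SAP. It needs no new data and no new analysis.
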